b. Uncontrolled trial. In the next phase, clinicians from 3 community programs were recruited to deliver the therapy: 1 psychiatric nurse practitioner, 1 masters' level and 1 bachelors' level counselor, 1 doctoral-level psychologist, and 1 addiction counselor intern. Only 1 had experience with CBT, PTSD, or manual-guided treatments. In addition to the didactic training, therapists received weekly supervision. Twice-monthly supervision was face-to-face, and twice monthly supervision was via telephone.

Eleven patients were enrolled in the treatment.¹⁸ Their average age was 34.4 years, all were Caucasian, and 91% were women. All patients met criteria for current PTSD (past 30 day symptoms) and had an average CAPS score of 73.9 (SD=13.9), indicating significant severity. With respect to baseline substance use, most patients were negative on current toxicological screens (urine and breath), but reported use on an average of 25 out of the past 90 days. Drug and alcohol severity composite scores on the Addiction Severity Index (ASI) were within a moderate to severe range of problem level.

Figure 3: CAPS Diagnosis Over Time

[figure not shown]
CAPS scores were significantly reduced from baseline to post-treatment (p<.001), and follow-up (p<.001). As seen in Figure 3, the number of cases who met criteria for PTSD dropped from 100% at baseline to 27% at post-treatment. At follow-up, 80% of cases no longer met diagnostic criteria for PTSD.¹⁸

[figure not shown]
There were no changes in positive toxicological data or in days of drug or alcohol use. However, there were significant decreases in the ASI severity composite scores between baseline and the follow-up periods (alcohol, p <.05; drug, p<.05). 18 With respect to retention, 65% of patients completed at least 8 sessions.

c. Randomized controlled trial. We are now piloting the treatment in a randomized controlled trial comparing CBT for PTSD with Individual Addiction Counseling (IAC); all patients receive addiction TAU. IAC was adapted from the Individual Drug Counseling manual used in the NIDA Cocaine Collaborative Study. IAC is an intervention that does not directly address PTSD symptoms, but instead its mechanism of action is focused on addiction and recovery. We selected IAC because it has an evidence-base for effectiveness with drug use disorders, is matched in attention and frequency to CBT, and its mechanisms of therapeutic action should not directly affect PTSD but instead reduce substance use.

Two therapists from 4 sites volunteered. Therapists were staff members at the program from which patients were being recruited. The therapists include 6 masters' level counselors (2 of whom were licensed alcohol and drug counselors) and 2 bachelors' level counselors (1 a licensed alcohol and drug counselor). Thus, these clinicians might be considered representative of the community addiction treatment program clinical workforce. Therapists trained in CBT were also trained in IAC and therefore crossed in the delivery of treatments. Thus, each therapist was randomly assigned cases for delivery of CBT or IAC.

To date, we have gathered baseline and post-treatment data on 8 cases in CBT, and 4 cases in IAC (30% of planned enrollment). The following preliminary findings are available at the time of this application. The

average age of participants in the CBT group was 40 years, 87.5% are women, and all are Caucasian. Among the IAC group, the average age was 35 years, 50.0% are women, and all are Caucasian. At baseline, all of the participants had PTSD, with an average CAPS score of 67.3 (SD=16.5) in the CBT group and 77.0 (SD=23.5) in the IAC group. The majority of patients had negative breathalyzer and urine toxicological screens (100% and 87.5%, respectively in CBT; 75.0% and 75.0% respectively in IAC). The CBT group reported significantly more drinking than the IAC group (29 out of 90 days vs. 1 out of 90 days), whereas the IAC group reported significantly more drug use (48 out of 90 days vs. 9 out of 90 days). Alcohol and drug severity scores (on the ASI) were in the moderate to severe range at baseline.

CAPS total scores decreased over time in both groups (Figure 4). Although there was not a significant group X time interaction, there was a significant reduction in PTSD severity only in the CBT group (p=.05) and not in the IAC group. After treatment, only 12.5% of the CBT participants met criteria for PTSD, in comparison with 50% of IAC participants, but the difference was not statistically significantly, most likely given the small sample size (Figure 5).

Figure 4: CAPS Total Score in CBT (n=8) and IAC (n=4)

Figure 5: CAPS Diagnosis in CBT (*n*=8) and IAC (*n*=4)

In terms of substance use, CBT had the largest impact on alcohol use and IAC had the largest impact on drug use. This may have been due to the fact that most participants in CBT drank and most in IAC used drugs. For the CBT group, there was a significant reduction in the number of days of alcohol use (p=.01) and a reduction in alcohol severity on the ASI alcohol composite (p=.05). Participants in the IAC group significantly reduced the number of days of drug use (p=.05), but not alcohol use, and had no significant changes on the ASI alcohol or drug composite scores.

In terms of retention, 69.2% of the patients in the CBT group completed at least 8 sessions and 80.0% of the IAC patients completed at least 8 sessions. On average, CBT completers attended 10.0 sessions and IAC completers attended 10.5 sessions.

d. Summary. These findings suggest that CBT for PTSD is a promising treatment for patients with PTSD and SUD in an addiction setting. CBT for PTSD is yielding greater improvement in PTSD diagnoses than IAC. It is less clear how well CBT for PTSD affects drug and alcohol use because of the imbalance of these problems between treatment arms in our sample to date. Both treatments have equivalent retention. CBT retention (69.2%) is consistent with the findings in the feasibility study (65%) and indicates good patient acceptability. Data on therapist adherence and competence continues to be favorable. All therapists are consistently delivering adequate quality CBT and IAC.

4. Summary

Given the scientific literature on the prevalence and consequences of PTSD in standard addiction treatment and a synthesis of the evidence for the available research-based therapies, it is clear that there is a need for a PTSD treatment that can be integrated into existing addiction services. Currently, there are no PTSD specific

treatments that have been evaluated for use in an addiction setting. We believe that our CBT for PTSD model can respond to this need.

There is a strong program of research behind the CBT for PTSD model. CBT for PTSD has been tested in three different populations, SMI patients, disaster survivors, and individuals seeking treatment for substance use problems. In each population, research has progressed from small, uncontrolled studies to randomized controlled trials. The logical next step is to conduct a randomized controlled trial of the CBT for PTSD in a VA setting, the single, largest medical provider in the country.

Our team is well-suited to conduct the trial. We bring together key members of the initial PTSD treatment model development team ([name] & [name]) with the investigator who took the lead on its adaptation for use in an addiction setting ([name]). Additionally, we have brought in leaders in VA on both the impact of PTSD on SUD treatment outcomes ([name]) and the effectiveness of SS in a VA addiction setting ([name]).

IV. RESEARCH DESIGN AND METHODS

A. Design

1. Overview

The proposed research will evaluate the effectiveness of the addition of a relatively simple, manual-guided CBT for PTSD to TAU in patients with co-occurring PTSD and SUD. One-hundred-sixty outpatients with comborbid PTSD/SUD will be randomly assigned to receive either CBT for PTSD in conjunction with standard TAU (n = 80) or TAU (n = 80) without additional individual treatment. Recruitment will target participants at three VA intensive outpatient addiction programs as well as participants with SUD and PTSD in those facilities who are not in the IOP. Participants will be assessed at baseline, post-treatment (approximately 4 months from baseline) and 6 month follow-up (approximately 10 months from baseline). Consistent with the goals of CBT for PTSD, the range of assessed outcomes includes both PTSD and substance use. Clinician adherence to the manual will be evaluated. Primary analyses will focus on the hypothesis that CBT for PTSD is more effective in reducing symptoms of PTSD than TAU.

2. Design considerations

We proposed an additive design because we think it optimizes the internal and ecological validity of the study. We are interested in determining whether care as usual can be improved by adding CBT for PTSD. Specifically, we want to test whether it is desirable to add a new therapeutic regimen to TAU for substance abusing patients with the additional problem of PTSD. Thus, all participants must receive usual care for substance abuse treatment in addition to the new treatment. One concern that is sometimes raised with additive designs is that they do not control for the amount of treatment. To control for this, an alternative treatment can be offered to equate time. However, we do not think amount of treatment would be a plausible explanation for the expected difference between the CBT and TAU arms because the amount of CBT we propose to add is small relative to the amount of time in TAU treatment. Depending on the site, Veterans will receive between 87 and 225 hours of care in their intensive outpatient program, not including any mental health treatment Veterans may receive outside of the program. On average, CBT would only add 4-11% more treatment, depending on the program. We will carefully measure treatment services of the participants with SUD and PTSD who are not enrolled in one of the two intensive outpatient programs.

Another reason to consider comparing an active treatment to an alternative one is if the question focuses on whether the new treatment improves outcomes obtained by another standard of care. Currently there is no standard of care to use as a comparison. Although Seeking Safety appears to be the most widely used treatment in VA for patients with comorbid PTSD and SUD, the empirical evidence suggests it is no more effective in improving PTSD than control conditions such as relapse prevention and women's health education. Therefore, treatment as usual can serve as the control for whether observed outcome is due to any addiction treatment versus the addition of CBT specifically.

B. Sample and Recruitment

1. Inclusion criteria

Eligible subjects will meet the following inclusion criteria: (1) At least 18 years old, (2) Diagnosis of current substance use disorder, (3) Diagnosis of PTSD confirmed by the Clinician Administered PTSD Scale with a

total symptom score of 45 or more, (4) English speaking, (5) Agree to be audio recorded, and (6) Willing and able to provide informed consent.

2. Exclusion criteria

Only three exclusion criteria will be applied in order to maximize sample representativeness. (1) Individuals with acute psychotic symptoms will be excluded if they are not well-connected with appropriate mental health services. (2) Patients with a psychiatric hospitalization due to a suicide attempt or severe suicide risk or who made an attempt in the last month regardless of hospitalization will be excluded. (3) Individuals with unstable medical or legal situations that would make completion of the study highly unlikely will be excluded. Thus, as previously noted, the proposed research will attempt to recruit as heterogeneous and representative a patient sample as possible.

3. Expected participant demographics and diagnostic characteristics

Based on information provided by PERC on SUD outpatients seen in specialized care throughout VA,⁵¹ about 95% of the patients are male, 24% are married, and the average age is 50 years old. About 52% are Caucasian, 41% African American, 7% Hispanic and 1% some other racial/ethnic group. Overall, 50% are Vietnam War era and 36% have a service-connected disability. With respect to diagnostic characteristics, 24% of SUD outpatients have a diagnosis of alcohol abuse/dependence only, 17% have a diagnosis of drug abuse/dependence only, and 45% have both disorders. Of the SUD outpatients seen in specialized care without alcohol or drug diagnoses, 4.5% had nicotine dependence as their only SUD diagnosis. About 60% had one or more other psychiatric disorders.

4. Sites

A search conducted by PERC identified 112 IOPs (i.e., SUD programs that offer at least 3 hours a day of treatment, 3 days per week). Of these 46 (41%) were excluded because they reported offering SS. We felt it was important to exclude sites that offered SS because it is not clinically indicated to have patients receive two trauma treatments simultaneously. From this search we selected, Tampa, FL and Syracuse, NY. These sites were selected because they treat more than 1,000 unique patients annually, were interested in conducting research at their sites, and were able to commit the necessary resources. We are also going to be using White River Junction VA as a site. White River Junction has the necessary resources, and will help bolster recruitment for the study.

5. Recruitment and enrollment

At least 1,000 unique Veterans were seen at each site over the last fiscal year. Thus we expect that each recruitment site will see at least 1,500 unique patients over the 18-month recruitment period. We used the VA performance measure on continuity of care to estimate the number of patients seen who have been actively engaged in the IOP for at least 3 days. This measure corresponds to the number of patients that have no SUD contact in the prior 90 days and then have at least 3 SUD visits within 30 days. Next we conservatively estimate that 30% of SUD patients will meet criteria for PTSD (see background). Finally, we included only those we believed will be interested. Randomized trials of brief interventions for SUD patients found that approximately 60% of patients eligible for study participation agreed to participate. Assuming similar rates of participation, we expect that at least 60% of eligible participants will be interested. However, our study will have adequate power even if only 33% of patients agree to participate (See Table 1, Section B6 below, and the Inclusion and Enrollment Table included under Human Subjects).

Table 1. Recruitment and Enrollment

Site	# of SUD patients with SUD visit in 2008	Expected # of SUD patients available over 18 months	# SUD patients "successfully retained" based on continuity of care performance measure	Estimated # of PTSD cases (30%)	If 60% patients interested	If 33% patients interested
Tampa, FL	1000	1500	801 (53.4%)	240	144	80
Syracuse, NY	1200	1800	869 (48.3%)	267	160	88

Below is a revised recruitment table, assuming we are approved to recruit within the next two months through the end of the proposed study. These numbers show potentially eligible participants assuming we open recruitment up beyond the IOP in the two facilities. Numbers of veterans with comorbid PTSD and SUD were provided by PERC for FY 2012. (Note: numbers would be higher if we receive a one year no-cost extension)

Site	Estimated # of PTSD cases with SUD (25%)	If 60% patients interested	If 33% patients interested
Tampa, FL	1274	764	420
Syracuse, NY	901	540	270

In August of 2013, we made the decision to add a third site, White River Junction VA. This decision was made to boost enrollment and because of the cost-effectiveness of this particular site.

6. Power analysis

We aim to have a sample that would yield .80 power in longitudinal analysis with generalized estimating equations model (a type of generalized linear mixed models) to find a standardized detectable difference from .4 to .5 between intervention and usual care, assuming alpha = .05, two-tailed. We assume that the correlation between repeated measures will be .60. The outcome of treatments will be measured at two points in time (3-month and 9-month) for each individual. The sample size for our primary hypothesis (difference in slopes by treatments) is based on Diggle, Liang, and Zeger, who developed a formula to calculate sample size for longitudinal studies with repeated measures to estimate the difference between slopes (or rate of change in CAPS as in this case) of two groups (m = size per arm):

$$M = 2(Z_{\alpha} + Z_{\beta})^{2} \sigma^{2} (1 - \rho) / (nS_{x}^{2} d^{2})$$

where $S_x^2 = \sum_j (x_j - \bar{x})^2 / d$, the within-subject variance of the x_j ; type I error α = 0.05, power β = 0.8 and the smallest meaningful difference d = $\beta_{1B} - \beta_{1A}$ and σ^2 = $Var(\epsilon_{ij})$ measures the unexplained variability in the response, $Corr(Y_{ij}, Y_{ik}) = \rho$ for all $j \neq k$, and n is the number of repeated measures per person.

Using this formula and based on these assumptions, we estimated the sample size needed. Table 2 shows how required total enrollment (both groups) would vary for a range of expected effects and if the true effect is larger or smaller than expected for a range of possible missing data scenarios.

Table 2. Enrollment Number N (total of two groups) as a function of effect size and rates of missing endpoints due to drop out and loss to follow-up

	Loss to Measurement						
actual effect size	10%	15%	20%				
.40	160	169	180				
.45	126	134	142				
.50	102	108	115				

We propose to enroll 160 subjects (80 in each treatment arm). The table shows we will have adequate power to find an effect as small as d = 0.4 if the percentage of missing data is 10%. And if the actual missing data is 20%, we still have enough subjects to detect an effect as small as .45. Because the primary analysis is intention-to-treat, we are basing our drop out on participants who are completely lost to measurement and not on those who do not complete treatment. We believe 20% is a conservative rate. Trafton et al (2003)⁷² successfully tracked and interveiwed 270 subjects participating in a multi-site opiod substitution treatment study at remote sites with a 90% follow-up rate at 6-months.

C. Study Treatments

Participants will be randomized to TAU plus CBT or TAU alone. Therapists who provide CBT will not provide TAU services to study patients. Ratings of CBT recordings (adherence and competence indexes) will confirm therapy integrity and independence.

1. CBT for PTSD

CBT for PTSD in addiction treatment programs is a simple, manual-guided individual therapy.⁵⁴ It consists of 3 learning and skill components designed to improve PTSD symptoms and substance use: (1) Patient education about PTSD and its relation to substance use and treatment; (2) Breathing retraining: A behavioral anxiety reduction skill; and (3) Cognitive restructuring: A cognitive approach and functional analysis of the link among emotions, cognitions and situations.

CBT for PTSD has 8 modules and is delivered over 8-12 hour-long individual sessions. We have set the completion of 8 sessions as the criterion for completion. The modules are listed in Table 3. A patient workbook is used in conjunction with the therapist manual, and, as with most cognitive behavioral therapies, the approach includes homework between sessions, patient education and self-monitoring, skill acquisition, implementation and practice, and developing self-efficacy about more adaptive and alternative cognitions and behaviors.

The first session begins with an orientation to the treatment and is followed by the development of a crisis and relapse prevention plan. Breathing retraining is introduced as a skill for managing and decreasing anxiety. It involves teaching patients how to slow their breathing in order to reduce hyperventilation by taking in normal breaths and exhaling slowly often while saying a soothing self-statement such as "calm" or "relax." Patients are reminded of the "fight or flight" response and how under threat people respond by taking in excess oxygen. Breathing retraining counteracts the automatic response and thereby slows down the intake of oxygen. After the therapist models the skill, the patient practices it first in session and then for homework under calm situations. Later, when patients become more proficient at the skill, they are encouraged to use the breathing skill to calm themselves when anxious.

Typically psycho-education is introduced in sessions 2 and 3. Psycho-education aims to provide patients with an understanding of PTSD symptoms and associated symptoms and is one way to normalize patients' reactions and reduce stigma concerns. If done properly, it can also provide a rationale for why patients are experiencing their distress, instill hope, and improve engagement.

Table 3: Organization of CBT for PTSD therapist manual: Module, topic and therapeutic focus

Module	Session	Topic	Therapeutic focus
1	1	Introduction	Relationship between therapy and addiction treatment program, substance use.
2	1	Crisis & Relapse Plan Review	Identify relapse triggers, cues, alternative coping tactics, pre- and post- slip/relapse contact persons and numbers.
3	1	Breathing Retraining	Develop skills to reduce tension and anxiety as specific relapse antecedent.
4	1-2	Psycho-education Part I: Core symptoms of PTSD	Examine relationship among trauma, PTSD symptoms, and substance use, by historical and current coping strategies.
5	2-3	Psycho-education Part II: Associated Symptoms of PTSD	Educate on specific relationships between substance use, addiction treatment compliance, use of peer recovery support groups and associated symptoms.
6	3-4	Cognitive Restructuring Part I: Thoughts & Feelings	Introduction to cognitive restructuring: Situations, feelings, common styles of thinking
7	4-7	Cognitive Restructuring Part II: Challenging Your Thoughts & Feelings	Acquisition and practice of cognitive restructuring, including evaluation of evidence for thoughts (that lead to PTSD-related feelings) and development of alternative thoughts and actions.
8	8-12	Generalization Training & Termination	Focus on generalization of skill acquisition, integration with addiction treatment and peer recovery support groups, and minimizing retraumatization potential.

Cognitive restructuring is taught over the next several sessions. First patients are introduced to the concept that people's emotional reactions to events are determined by their interpretations of those events. These interpretations may be influenced by other events the person has experienced, including traumatic events. Patients are informed that different types of negative feelings are associated with specific types of thoughts, which are often automatic and occur outside of their awareness. Patients identify upsetting situations and the associated thoughts and feelings.

Next patients are introduced to the cognitive distortions (called common styles of thinking) that may result from basing current thinking on past traumatic experiences. For example, patients who have experienced traumatic events often "catastrophize" or "overestimate risk" in situations in which there is no reason to suspect that something bad will happen. Patients are apprised of common problematic thinking styles and are helped to identify and correct distortions related to negative emotions.

Thereafter, patients are introduced to a five-step cognitive restructuring (CR) method for dealing with negative emotions. These steps are summarized on a worksheet, which is used both in the session with the therapist and practiced by the patient outside of the session on his or her own or with the help of another person. The five steps of CR are (1) Describe the situation, (2) Identify the negative feeling, (3) Identify the thought related to the feeling, (4) Challenge the thought, and (5) Take action. Patients practice CR for the remainder of the treatment sessions. The goal is to help patients move from learning CR as a skill to applying it to their disaster-related thoughts and from using the formal CR worksheet to completing the steps in their head when they are in an upsetting situation or immediately after it is over.

The last session focuses on generalization training and termination to ensure that the patient is able to use cognitive restructuring on their own outside of sessions, to review treatment gains, and discuss any plans to meet ongoing or potential needs that may arise.

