Clinician Administered PTSD Scale (CAPS): The CAPS⁷⁸ is a structured diagnostic interview and is widely regarded as the gold standard for determining a diagnosis of PTSD. It has excellent reliability and validity^{78, 79} PTSD diagnosis on the CAPS is based on meeting the DSM-IV symptom criteria, as well as having a minimum severity score of 45. Symptoms are considered to be present when they have a frequency rating of at least 1 and an intensity rating of at least 2.⁷⁹ Ratings will be based on current symptoms (past month).

Structured Clinical Interview for DSM-IV-Patient Edition with Psychotic Screen (SCID-P): Substance use disorders and other Axis I psychiatric diagnoses (other than PTSD) will be established using the SCID. 80-82 The SCID is a semi-structured interview that is widely accepted as the gold standard for establishing adult psychiatric diagnosis. 82 Our research center has extensive experience training research interviewers and using the SCID with a wide range of clinical populations, including patients with co-occurring psychiatric and substance use disorders.

3. Outcomes

Participants' treatment outcomes will be assessed at baseline, post-treatment for the CBT group (approximately 3 months after baseline) and 3 months after baseline for the TAU group, and at 6 month follow up (approximately 9 months after baseline).

CAPS: PTSD severity, as measured by the CAPS (see above) will serve as the primary outcome measure. CAPS severity is calculated by summing the frequency and intensity score for each item. We will also examine the percentage of patients who show clinically significant change on the CAPS, as defined as a decrease of 10 points or more⁷⁹.

PTSD Checklist (PCL): A secondary measure of PTSD will be the PCL.⁸³ The PCL is a widely used self-report measure that assesses the 17 DSM-IV PTSD symptoms. Responses to these questions are on a scale of 1 to 5 ("not at all" to "extremely"). The PCL has excellent psychometric properties. It will be administered at all assessments, and at every other treatment session to monitor symptoms.⁸³

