Individuals providing consent and meeting inclusion/exclusion criteria as confirmed by the baseline assessment will then be randomized. We will perform block randomization (block size of 2, 4, and 6) in allocating subjects to treatments. Moreover, stratified block assignment will be used, so that each treatment group will be balanced on type of substance use (alcohol only versus drug with or without alcohol, 2 categories), whether the patient has severe PTSD (2 categories), and the site of treatment (2 sites).

Patients who are randomized to CBT for PTSD will receive 8-12 individual sessions of CBT for PTSD. These sessions will be offered once or twice per week depending on patient and therapist availability. All participants will receive TAU. For patients assigned to CBT, approximately one week after the end of treatment patients will be given the post-treatment assessment. Patients in TAU will be assessed 4-5 months after the baseline. Six months from the post assessments all participants will receive the 6 month follow-up assessment. Assessors will be blind to treatment condition. Patients will be paid \$30 for the post-treatment and follow up assessments. Patients will receive a reminder letter about their first appointment (and about subsequent appointments if requested.) Patients who miss a session of treatment or assessment may be sent a letter of contact, if study staff are unable to reach them by phone.

G. Data Analysis

This study is designed as a two-arm, parallel comparison of two therapies in the treatment of PTSD in patients who are receiving care in a VA intensive outpatient program for substance abuse or patients with comorbid substance use and PTSD. In designing this study, there are analysis issues that require special attention, such as handling of missing data, adjustment for loss-to-follow-up, and serial correlation for sample size calculation. The strategy for data analysis flows from the goals of the study, and in turn defines the statistical tests and sample size projections.

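### Table 2 cannot be reproduced from the difference-in-slopes formula it is said to come from; at d = .40 with 10% loss that formula needs 168 to 174 subjects, not 160

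*Combined protocol and SAP*

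**What the plan says.** Section IV.B.6 sets two-sided alpha .05, power .80, a standardized difference of .4 to .5 and a correlation of .60 between repeated measures. It gives the measurement plan as "The outcome of treatments will be measured at two points in time (3-month and 9-month) for each individual". It then cites a published formula used to "estimate the difference between slopes (or rate of change in CAPS as in this case) of two groups", prints it, and says of Table 2: "Using this formula and based on these assumptions, we estimated the sample size needed".

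The text below Table 2 draws two conclusions for 160 enrolled. With 10% missing data, "we will have adequate power to find an effect as small as d = 0.4"; and "if the actual missing data is 20%, we still have enough subjects to detect an effect as small as .45".

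Visit times differ between sections:

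- IV.A.1 (Overview): "post-treatment (approximately 4 months from baseline) and 6 month follow-up (approximately 10 months from baseline".
- IV.E.3 (Outcomes): post-treatment at about 3 months, "and at 6 month follow up (approximately 9 months after baseline".
- IV.F (Procedure): "Patients in TAU will be assessed 4-5 months after the baseline", with the last visit six months after that.

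Section IV.G.1 displays a linear model with Time, Group and their interaction, and takes the interaction (the difference in slopes) as the quantity of interest.

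**The concern.** Table 2 is the only basis for the sample size, and the claim of adequate power at d = .40 rests on its 160 cell. A slope formula depends on when the outcome is measured and on the time over which d accrues. The section gives no time span for d, and the protocol gives several visit schedules. If the table came from a formula for some other contrast, the stated .80 does not belong to the primary test, and a reader cannot tell which test it does belong to.

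**Working it through.** **Inputs.** From IV.B.6: z = 1.960 (two-sided .05) and 0.842 (power .80), so K = 2(1.960 + 0.842)² = 15.698; ρ = .60. The difference is standardized, so σ² = 1. Allocation is 1:1.

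**What Table 2 implies.** Write total enrollment as N = 2C / [d²(1 − loss)]. The values of C that round to all nine cells run from 11.489 to 11.526.

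**The named formula.** It is m = K(1 − ρ) / (n·Sx²·d²) per arm. Two readings are needed:

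1. *Divisor of Sx².* It is printed as d, which may be a typing or text-extraction error. Taken literally, N would fall as 1/d, giving a ratio of 1.25 between d = .40 and d = .50. The table's ratio is 160/102 = 1.57, close to (.50/.40)² = 1.56. The literal divisor also gives totals of only 22 to 35 at d = .40 with 10% loss. I use n.
2. *Scale of d.* I take the between-arm difference in change over the measured span, which fits the change-in-mean-difference test in IV.G.1.

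With times divided by the span, n·Sx² is the sum of squares SS and C = 15.698 × .40 / SS. For visits 0, 3, 9 the scaled times are 0, .333, 1 with mean .444. Then SS = .1975 + .0123 + .3086 = .5185, C = 12.11, and N = 2 × 12.11 / (.16 × .90) = 168.

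| Visits (months) | SS | C | N at d = .40, 10% loss |
|---|---|---|---|
| 0, 3, 9 | .5185 | 12.11 | 168 |
| 0, 4, 10 | .5067 | 12.39 | 172 |
| 0, 5, 11 | .5014 | 12.52 | 174 |
| 3 and 9 only | .5000 | 12.56 | 174 |
| Table 2 | – | 11.489–11.526 | 160 |

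At 10/15/20% loss:

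| d | Table 2 | 0, 3, 9 | 0, 4, 10 | 3 and 9 |
|---|---|---|---|---|
| .40 | 160/169/180 | 168/178/189 | 172/182/194 | 174/185/196 |
| .45 | 126/134/142 | 133/141/150 | 136/144/153 | 138/146/155 |
| .50 | 102/108/115 | 108/114/121 | 110/117/124 | 112/118/126 |

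**Other readings at d = .40, 10% loss.** None gives 160:

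- Divisor n − 1: 87 to 116.
- One-sided alpha: 132 to 137.
- Inflating by (1 + loss): 166 to 173.
- d over another span in the documents (3, 4, 6 or 9 months): 19 to 392.

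**What a match would take.** Any one of these would do it, and none is stated: ρ of .62 to .63; a span for d of 8.8 months (visits 0, 3, 9), 9.6 (0, 4, 10) or 5.7 (3 and 9); or a post-treatment visit at about 24% of follow-up (month 2.1 of 9).

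**A formula that does match.** For a difference in time-averaged means with three measurements, C = K(1 + 2ρ)/3 = 15.698 × 2.2/3 = 11.512. This gives 160/169/180, 126/134/142 and 102/108/115, which is every cell.

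**Power at N = 160.** For the slope test with a linear effect, power = Φ(√[m·d²·SS / (2(1 − ρ))] − 1.960).

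- d = .40, 10% loss (m = 72): for visits 0, 3, 9 the root is √(72 × .16 × .5185 / .80) = 2.733, so power is .78. For 0, 4, 10 it is .77, and for 3 and 9 it is .765. The detectable d is .41 to .42.
- d = .45, 20% loss (m = 64): .83, .82 and .81.
- Baseline-adjusted single visit, C = K(1 − .36) = 10.05: the d = .40 row is 140/148/157, with power .85 at 10% loss and .81 at 20%.
- Slope model with no baseline group difference: the d = .40 row is 139/147/157, with power again .85 and .81.

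**The case against.** The arithmetic is not in dispute. There are three arguments for treating the mismatch lightly.

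*Timing in the CBT arm.* IV.F offers 8 to 12 sessions once or twice a week, with assessment about a week after the last one. That puts the CBT post-treatment visit at roughly weeks 5 to 13, or 16% to 33% of follow-up, a range that includes the 24% needed. The formula then gives 151 to 168, and about 162 at week 9. This is true, but it describes one arm over a range. The formula assumes common times, TAU is assessed at 4–5 months, and the power section itself says 3 and 9 months.

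*Residual variance.* The formula calls σ² unexplained variability, and IV.G.1 allows covariates that reduce it. A σ² of about .95 (visits 0, 3, 9), .93 (0, 4, 10) or .92 (3 and 9) would reproduce the table. No such value is given, and σ² = 1 is the natural reading of a standardized difference.

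*Consequence.* The detectable d of .41 to .42 still lies inside the stated .4 to .5, the claim at d = .45 with 20% loss survives, and 160 is ample under baseline adjustment. All of this stands. It limits the size of the problem, but it does not make the table the output of the formula named for it.

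**Conclusion.** The concern holds. Table 2 does not follow from the formula and assumptions given for it under any common visit schedule stated in the protocol. On the slope formula the required enrollment is 5% to 9% higher (168/160 = 1.05; 174/160 = 1.09), and the claim of .80 power at d = .40 with 10% loss becomes .765 to .78.

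Those replacement figures rest on divisor n, d taken over the measured span, σ² = 1, exchangeable correlation of .60 and a linear effect. The failure to match does not depend on the first two, since the alternative readings miss by more.

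The time-averaged formula as the source is an inference from a nine-cell match. If correct, the table sizes an average level that counts baseline, where IV.G.1 expects no difference, instead of the slopes named as primary.

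This should be fixed because the stated power cannot be tied to the primary test. It does not show that the trial is too small: 160 is slightly short for the displayed slope model and enough for a baseline-adjusted contrast.

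**What to change.** In IV.B.6, name the contrast to be tested, the measurement times and the time span to which d refers, and correct or confirm the divisor of Sx². Use the same visit times in IV.A.1, IV.E.3 and IV.F, or say which set the calculation uses. Recompute Table 2 for that contrast and restate the power or detectable d at N = 160 in the text below it.

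- If the slope test with a Group term is kept: state about .77 to .78 power at d = .40 with 10% loss (.765 if only the 3- and 9-month visits enter), or a detectable d of .41 to .42.
- If a baseline-adjusted contrast at one named visit is made primary: the d = .40 row becomes 140/148/157, with power .85 at 10% loss and .81 at 20%.

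The cost is one paragraph and one table, with no added patients. The only downside is a slightly less favourable stated figure if the slope test is kept; there is none if the baseline-adjusted contrast is named.
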